**Table 8. Anticipated costs, savings and benefits for cost-effectiveness analysis**

| HITSystem 2.0 Intervention Costs  | Anticipated Cost Savings   | Anticipated Benefits                         |
|---|--|--|
| training, licensing, internet, computer/modem, implementation support
*costs to health system may increase with higher rates of VL testing | Reduced: delayed/un-returned VL results, detectable VL results w/out clinical action, poor maternal ART adherence, pediatric infections and associated costs | QALY saved (infants)
QALY saved (mothers) |

#### 6.0 Data storage and management

All relevant clinical data at intervention sites will be captured through the HITSystem's online, automated system which produces output in Excel format. Patient specific information (including infant and mother demographics; mother's phone number and patient tracing information; PMTCT appointment attendance, maternal viral load testing and results, ART adherence, infant's date of birth; infant weight and gestational age at delivery; dates of sample collection, HIV test processing, results return, mother notification; and date of infant ART initiation for positive infants) will be entered by the Mentor Mother at the hospital during the first and subsequent PMTCT consultations to capture relevant demographic and clinical data and laboratory results. *Data will be de-identified* and maintained for each mother-infant pair within the password-protected HITSystem using a numeric ID to protect the identity of all participants. The site coordinators will routinely visit HITSystem sites for data quality assurance. At non-HITSystem sites, we will use individual patient (mother and infant) files, augmented by available hospital paper-based registers and the national laboratory online database to collect relevant routine clinical data. Patient records will be filled out by personnel performing the respective actions. The site coordinator will routinely visit non-HITSystem study sites to conduct retrospective record review of patient records and

enter relevant study data into a secured electronic database. As with HITSystem data, each mother-infant pair will be identified by a numeric study ID to protect their identity.

At enrollment, at the “delivery” VL test, and at the postpartum VL test, participants will take a brief survey assessing individual characteristics, partner support, depression, and interpersonal violence. Mentor mothers will conduct these surveys on paper forms. Site coordinators will then enter the responses from paper forms into a *secured electronic database*. Additional paper-based study logs kept at study sites will document study enrollment, enrollment refusal, adverse events that occur as a result of the study, and communication between clinical or study staff and participants. Hospital or national-level events that may impact clinical care and study operations will be documented across all sites (intervention and control). In addition, separate study logs will be used to document data related to research-specific viral load sample collection at both intervention and control sites at delivery, and at >7 months postpartum for those disengaged from care, including VL sample collection date and results. Logs will be filled out by personnel performing the respective actions. The site coordinator will collect study logs and surveys routinely at all study sites and enter them into a *secured electronic database*.

All dried blood spot samples collected for research-related viral load tests will be labeled with the participant’s unique study ID and sent to an independent laboratory (KEMRI CDC) for sample processing. All samples will be processed per the laboratory’s established procedures. Results will be mailed back to the study team and maintained in a secure electronic database.

All study staff will be trained to promote standardized and objective collection and recording of participant information. Study personnel will review data entered in the HITSystem and other study data collection tools for legibility, consistency, and completeness. All data will be stored in a password-protected database that is backed up through a secure offsite connection. All HITSystem data (PMTCT and EID) will be stored and backed-up on secure servers in Kansas City, USA. We are currently in the process of identifying a Kenya-based server for local data storage. Every 24-hours study data will be backed up on a *secure cloud-based server*, which the PIs from each institution and key study personnel (biostatistician and study manager) will have access to through *password-protected login*. County officials, hospital administrators and MCH departments will be able to access de-identified progress and performance data from their facility/region by using their read only, site-specific login and password. All data collection, storage, and use will be compliant with Kenya’s Data Protection Act of 2019.

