**Participant surveys:** A brief enrollment survey will collect same demographic and clinical data at control sites (without HITSystem 2.1) in addition to patient-level data regarding PMTCT information, motivation, partner status and support, HIV disclosure, depression (modified Edinburgh postnatal scale), and risk of violence (both arms, Appendix 2A). Repeated surveys after delivery and 6m postpartum (for VL sample collection described in Objective 2, both arms) will include these same patient-level measures to assess any changes that may mediate or moderate intervention impact (Appendices 2B & 2C). Participants will be compensated 200 KES for completion of each survey.

**Facility assessment form** (Appendix 2D) will be completed at the beginning, mid-point and end of study implementation to assess average resource level, annual PMTCT volume, and PMTCT provider-patient ratios.

**Provider surveys:** At baseline and again at the end of the study period, providers in both arms will be asked to complete a short survey (Appendix 2E) assessing provider role/ department, level of experience, knowledge and motivation regarding current PMTCT guidelines, and barriers and facilitators to provision of complete PMTCT services. We estimate n=5 providers per site to complete the survey for a total of n=60 providers (n=30 intervention, n=30 control). Prior to completing the survey, providers will complete an informed consent (Appendix 2C). Providers will be compensated 500 KES for completion of each survey.

**Supportive Supervision Visits** will occur monthly at all sites. During these visits, Site Coordinators will provide technical assistance and retraining, review study materials (informed consent forms, surveys), and review data for completeness and accuracy. The monthly frequency of site visits approximates programmatic HITSystem 1.0 implementation support in Kenya.

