**Effectiveness:** Objectives 1 & 2 assessing complete PMTCT retention and viral suppression will evaluate effectiveness. We will also measure adverse outcomes as a result of the program.

**Adoption:** At the *facility-level*, we will note any facilities which decline study participation and reasons for refusal. Among participating hospitals, the facility assessment form – filled out pre-mid-post study implementation – will collect data regarding resource level, patient-provider ratios, annual volume, implementing partners and outside support, and other facility details will be used to assess representativeness with Kenyan health care facilities. At the *provider-level*, adoption will be evaluated through provider surveys, assess the degree to which providers used HITSystem 2.1, determine which components were most beneficial, and assess facilitators and barriers to HITSystem 2.1 adoption. *Patient surveys* will similarly assess utility of SMS outreach components and suggestions to optimize benefit.

**Implementation:** Any changes to HITSystem 2.1 programming or study protocols will documented in research logs and/or through IRB amendments. Any changes to HITSystem 2.1 implementation at the hospital-level (i.e. location changes of desktop to better suit workflow, changes in key users, etc) will also be documented in study logs to guide implementation recommendations. We will review all HITSystem texting logs during the implementation period to assess fidelity of the SMS component by calculating the proportion of SMS sent according to participant preference (correct frequency and content) and the proportion received by a functioning mobile number. We will compare this with participants' reports of the number of SMS received as part of the study and the reasons for these SMS, which will be collected as part of the patient surveys.

**Maintenance:** Continued HITSystem 2.1 enrollment after the study enrollment period has ended (years 3-5) and utilization after the study follow up period (year 4-5) will serve as an indicator of system maintenance. In Years 3-5, the US-based study manager will compare the overall number of HITSystem 2.1 enrolments with PMTCT registers to assess if reach is being maintained. Using the HITSystem 2.1-generated alerts report, s/he will document the number and duration of provider alerts as a measure of system use.

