Participants will be informed of these conditions during the informed consent process and the precautions described above will be employed to mitigate any risks to participant confidentiality, privacy, and safety.

**Intimate Partner Violence (IPV).** If a case of IPV is reported during study engagement (per routine surveys including questions to assess risk and experience of IPV), the participant will be counseled on options for seeking care and referred to the nearest service provider, including referral for legal action. Participants who report IPV over the phone (via study contact or mentor mother) will be encouraged to visit the clinic for an in-person consultation and will also be offered a home visit by a mentor mother. All study staff will be trained to ask for and identify signs of IPV among pregnant and postpartum women living with HIV. Any form of IPV during the study period will be reported as an adverse event.

**Psychological Distress.** The informed consent process will be carefully designed to prepare women for the Early Infant Diagnosis testing process after they deliver and the possibility of an HIV positive diagnosis for their infants. In addition, the existing use of peer counselors to support pregnant women and mothers to consider care and treatment options for themselves and their infants, and to process their and their infant's HIV positive diagnosis will continue to be employed in the study. If additional support and follow-up services are needed, the PMTCT/EID provider will arrange for additional on-site counseling.

**Reduction of Physical pain and/or discomfort.** Dried blood spot (DBS) samples will be collected for all research-related viral load testing. Providers are most experienced with this form of blood sample collection and thus may be more proficient in collecting samples in this manner with less pain and discomfort for the participant. Training on VL testing procedures will be reinforced to minimize risk of collection errors and need for repeat sample collection.

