## Risk of Violence

For each of the following statements (21-24), choose the answer which best indicates how often each has occurred in the past 12 months.

|   | Never | Rarely | Sometimes | Frequently |
|---|-------|--------|-----------|------------|
| 21. In the past 12 months, has your partner ever insulted you or made you feel bad about yourself?                          |       |        |           |            |
| 22. In the past 12 months, has your partner ever hit you, kicked you, dragged you, or beaten you up?                        |       |        |           |            |
| 23. In the past 12 months, has your partner ever hit, kicked, dragged or beaten your child?                                 |       |        |           |            |
| 24. In the past 12 months, has your partner ever physically forced you to have sexual intercourse when you did not want to? |       |        |           |            |

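### Three conflicting adverse event rules leave logged harm counts inconsistent and not safely comparable between arms

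*Combined protocol and SAP*

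**What the plan says.** Three places state what counts as harm.

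- **Section 6.0, Data storage and management.** Paper logs at the sites will document, among other things, "adverse events that occur as a result of the study".
- **Section 8.0, Intimate Partner Violence paragraph.** "Any form of IPV during the study period will be reported as an adverse event". The same paragraph has cases come to light through the routine surveys.
- **Objective 3 methods, Effectiveness paragraph.** "We will also measure adverse outcomes as a result of the program".

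Violence is also measured by survey. Section 6.0 says that at enrollment, at the delivery viral load test and at the postpartum viral load test, "participants will take a brief survey assessing individual characteristics, partner support, depression, and interpersonal violence". The Participant surveys paragraph applies this to both arms and says the repeat surveys "will include these same patient-level measures to assess any changes that may mediate or moderate intervention impact". The violence block in each of Appendices IIA, IIB and IIC asks the woman to "choose the answer which best indicates how often each has occurred in the past 12 months".

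The Objective 1 secondary outcomes include infant HIV transmissions and maternal and infant deaths, with no causality condition.

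**The concern.** The first and third rules count an event only if someone attributes it to the study or to HITSystem. The second does not. A causality condition is not neutral between arms: an intervention site can have an event caused by the program, and a control site can hardly have one. The documents do not say who judges causality. Section 6.0 has logs completed by whoever carried out the activity, and the Staffing paragraph has mentor mothers trained for their own arm, so site staff know the allocation.

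Section 8.0 itself names inadvertent disclosure of HIV status and IPV among the risks to be mitigated. If logged counts depend on which rule a site follows, a difference between arms could reflect attribution practice rather than harm. Equal counts would not show that harm was absent.

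**Working it through.** No arithmetic is needed for the conflict itself. The check is to take one event and apply each rule.

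| Event | Section 8.0 (any IPV) | Section 6.0 (study-caused) | Objective 3 (program-caused) |
|---|---|---|---|
| IPV, intervention site, judged due to an SMS | counts | counts | counts |
| IPV, either arm, judged due to a study home visit outside HITSystem | counts | counts | does not count |
| IPV, either arm, judged unrelated | counts | outside the stated scope | does not count |
| Unintended disclosure, either arm | not addressed | counts only if judged study-caused | counts only if judged program-caused |

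The first three rows show that IPV is treated differently by the three rules. No passage reconciles them or gives a general definition of an adverse event. The last row is a gap rather than a contradiction, because the Section 8.0 rule covers IPV only.

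**Can the surveys stand in for the logs?** Partly. The same four violence items are put to both arms at enrollment, delivery and 6 months postpartum, with no question about cause, so prevalence can be compared by arm. Timing is the limit:

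1. The enrollment survey looks back 12 months and so describes the time before the study.
2. The delivery survey is done within 4 weeks of delivery. A 12-month window less at most 4 weeks reaches back at least about 11 months before delivery, which is longer than a pregnancy. Women enroll during pregnancy, so this window opens before enrollment.
3. The survey at 6 months postpartum reaches back to 12 − 6 = 6 months before delivery. It overlaps the delivery survey's window, and for a woman who enrolled later than that it also includes time before enrollment.

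The items record frequency categories, not dates. They give 12-month prevalence at each visit, not events in the study period, although Section 8.0 relies on these surveys to detect IPV for a rule defined by the study period.

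**Disclosure.** The surveys ask both arms whom the woman has told. The item on a relative or friend discovering her status appears only in the intervention-only blocks of Appendices IIB and IIC and refers only to SMS. Section 8.0 names home visits as a disclosure risk, and the tracking procedure under Objective 2 does not restrict them to one arm. The home-visit form (Appendix IIF) has no item for a disclosure that results from the visit.

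**Analysis.** The statistical analysis paragraphs for Objectives 1, 2 and 3 specify no between-arm comparison of adverse events. The factors listed under Objective 1 for examination of change over time do not include violence.

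**The case against.** The passages can be read together. Section 6.0 lists what additional paper logs contain; it does not say that nothing else may be logged, or that the logs are the only adverse event record. Section 8.0 can be taken as a specific rule for IPV, served by surveys that are entered separately. The Objective 3 sentence belongs to an implementation evaluation, where asking about adverse outcomes of the program is natural, and Table 7 lists only the two primary outcomes under Effectiveness. No between-arm harm analysis is planned, so no planned analysis fails.

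Much of this stands, and it rules out several stronger readings that a reader might infer:

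- *That the arms cannot be compared on harm.* They can be compared on survey-reported violence, on deaths and on infant infections, none of which passes through a causality filter.
- *That the rules also conflict on disclosure.* The any-cause rule does not mention disclosure. The problem there is the absence of a specific rule and of a control-arm item.
- *That reports to the ethics committees would differ greatly.* The protocol text describes committee approval, not adverse event reports to them. Consent pages are not available, so what they say on harms cannot be judged.
- *That staff operating the system decide what counts.* This is plausible, but the documents name no assessor.

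The objection does not remove the conflict in wording. A site following Section 6.0 as written need not log an IPV event it thinks unrelated, while Section 8.0 requires that event to be reported as an adverse event, and no instruction says which record holds it. The surveys do not fill the gap because of their look-back window.

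**Conclusion.** The concern holds for the adverse event rules and the counts drawn from the logs. The three rules conflict on IPV. Two of them filter by attribution, and the program-based one can hardly yield events at control sites. Logged harm counts are therefore inconsistent and not safely comparable between arms. The surveys support a between-arm comparison of IPV prevalence but do not isolate events in the study period, and discovery of HIV status is asked about in one arm only and for SMS only.

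The size cannot be given as a number of events: the documents state neither an IPV rate nor the share of events that staff would attribute to the study. The conclusion rests on the wording alone and on one assumption, that staff apply the log rule as written. The primary outcome analyses are unaffected.

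**What to change.** Reconcile Section 6.0, the IPV paragraph of Section 8.0 and the Effectiveness paragraph of Objective 3 to one rule that reads the same in both arms:

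1. Log every reported IPV event and every unintended disclosure of HIV status in both arms, with its date and regardless of cause.
2. Record relatedness to the study and to HITSystem as a separate field, and state who completes it.
3. Add to the control-site surveys an item on unintended discovery of HIV status, and word it in both arms so that it is not confined to SMS.
4. State a summary of all-cause events by arm, descriptive where events are rare. Include the existing survey violence items, labelled as 12-month prevalence, and the deaths already collected under Objective 1. List related events separately.

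The cost is more log entries, a changed survey item with its Swahili and Luo versions, and a short addition to the analysis text. The sample size section shows that enrollment is under way and already closed at two sites, so the date of the change should be recorded and logs from before it should not be pooled with later ones without comment.

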## 7.0 Timeframe/duration of the study

We anticipate the study will last for five years, including a 6-8 month start up period for site selection and matching, IRB approvals, hiring and training, followed by a 1.5-year period to accrue the sample size of n=96 eligible women per site.

This 1.5-year accrual period will allow lower volume facilities (i.e. those with 4-5 HIV-positive pregnant women enrolling per month) to achieve the sample size. If a site fails to reach n=96 participants after 18 months, enrollment will be extended and the “maintenance monitoring” period at that facility will be shortened to achieve the target sample size. Prospective follow-up of all mother-infant pairs (pregnancy through postpartum) and provider interviews will require an additional year, after enrollment stops. Data cleaning and analyses will begin midway through Year 4, with dissemination at end of Year 5, see Table 9.

Table 9. Study Timeline

|                              | Year 1 |   |   |   | Year 2 |   |   |   | Year 3 |   |   |   | Year 4 |   |   |   | Year 5 |   |   |   |
|------------------------------|--------|---|---|---|--------|---|---|---|--------|---|---|---|--------|---|---|---|--------|---|---|---|
| Quarters                     | 1      | 2 | 3 | 4 | 1      | 2 | 3 | 4 | 1      | 2 | 3 | 4 | 1      | 2 | 3 | 4 | 1      | 2 | 3 | 4 |
| Study start-up               |        |   |   |   |        |   |   |   |        |   |   |   |        |   |   |   |        |   |   |   |
| Enrollment, sample accrual,  |        |   |   |   |        |   |   |   |        |   |   |   |        |   |   |   |        |   |   |   |
| Follow sample through 6m pp, |        |   |   |   |        |   |   |   |        |   |   |   |        |   |   |   |        |   |   |   |
| Maintenance monitoring       |        |   |   |   |        |   |   |   |        |   |   |   |        |   |   |   |        |   |   |   |
| Data cleaning and analyses   |        |   |   |   |        |   |   |   |        |   |   |   |        |   |   |   |        |   |   |   |
| Dissemination with partners  |        |   |   |   |        |   |   |   |        |   |   |   |        |   |   |   |        |   |   |   |

## 8.0 Ethical considerations: human subjects

### Potential Benefits:

In spite of a global concerted effort, uptake and retention in quality, evidence-based PMTCT and HIV care continues to be suboptimal. This study will include vulnerable populations – HIV-infected mothers and HIV-exposed or HIV-infected infants living with severely constrained resources. Participation does have the potential for direct benefit. Complete PMTCT and guideline-adherence VL monitoring and clinical management has the potential to improve HIV+ women’s health and prevent transmission of HIV to their infants. If transmission does occur, earlier linkage to infant HIV testing can allow for earlier treatment initiation, which has been shown to improve outcomes in HIV-infected infants. In addition, for those who miss their postpartum VL test, follow up efforts to obtain a sample and share VL results has the potential to directly benefit mother-infant pairs (especially if VL is high) by re-engaging them in care and facilitating action to address high viral load.

Potential risks and steps taken to mitigate risks:

**Loss of confidentiality.** To protect confidentiality, the following steps will be taken: Study staff will be trained regarding the need to strictly protect confidentiality; this will also be reinforced with the clinic staff. Prior to starting the study, we will meet with clinic staff and peer counselors to identify any additional strategies that could be taken in that particular setting to help improve participant confidentiality. This includes strict adherence to protocols for the content of HITSystem text messages sent to caregivers and procedures for those engaged in patient tracing in the community. Extensive measures have been taken in the development of the HITSystem to customize text messages to avoid risk of disclosing the caregivers' or their infants' HIV status or increased stigma. These steps included focus groups to help guide the development of the messages and pilot testing the content of text messages. Messages sent by the HITSystem never indicate that the hospital visit is related in any way to HIV. Access to HITSystem will be restricted only to research staff directly involved in implementation and evaluation of the study. All electronic data will be de-identified, and recorded through use of a numeric ID for each participant (HIV+ woman and her HIV-exposed or HIV-positive infant participating in Objectives 1 and 2. Access to the HITSystem will be password protected and only permitted after completion of training. The link between participant name and study ID and HITSystem ID is known only by the research staff member involved in participant enrollment or the PMTCT/EID provider who has an established care relationship with the woman and her infant (Objectives 1&2 HIV+ mothers/infants). The record linking patient name, study ID, and HITSystem ID will be securely stored by the provider in the password protected computer designated only for study use. De-identified data will be used for all analyses and results.

Home visits to track LTFU participants for VL testing present an additional risk of inadvertent HIV status disclosure to community or household members. Study staff conducting home visits will be trained on protection of confidentiality, including instructions to reschedule any home visit if privacy is perceived to be compromised. In the event a participant relocated or is not home, any conversation with household members will only refer to a well-baby visit. A "home visit" checklist will be used to reinforce these procedures.

Participants will be informed of these conditions during the informed consent process and the precautions described above will be employed to mitigate any risks to participant confidentiality, privacy, and safety.

**Intimate Partner Violence (IPV).** If a case of IPV is reported during study engagement (per routine surveys including questions to assess risk and experience of IPV), the participant will be counseled on options for seeking care and referred to the nearest service provider, including referral for legal action. Participants who report IPV over the phone (via study contact or mentor mother) will be encouraged to visit the clinic for an in-person consultation and will also be offered a home visit by a mentor mother. All study staff will be trained to ask for and identify signs of IPV among pregnant and postpartum women living with HIV. Any form of IPV during the study period will be reported as an adverse event.

**Psychological Distress.** The informed consent process will be carefully designed to prepare women for the Early Infant Diagnosis testing process after they deliver and the possibility of an HIV positive diagnosis for their infants. In addition, the existing use of peer counselors to support pregnant women and mothers to consider care and treatment options for themselves and their infants, and to process their and their infant's HIV positive diagnosis will continue to be employed in the study. If additional support and follow-up services are needed, the PMTCT/EID provider will arrange for additional on-site counseling.

**Reduction of Physical pain and/or discomfort.** Dried blood spot (DBS) samples will be collected for all research-related viral load testing. Providers are most experienced with this form of blood sample collection and thus may be more proficient in collecting samples in this manner with less pain and discomfort for the participant. Training on VL testing procedures will be reinforced to minimize risk of collection errors and need for repeat sample collection.

